6.1.3.1 Model checking procedures

Subjects withdrawn for any reasons other than safety and tolerability may be replaced on a case by case basis.

If one of the 23h 15 min and 23h 45 min values are missing (or set to missing) then the remaining non-missing value will be taken as trough FEV1. If both values are missing, or if the subject withdrew from the study, regardless of the reason for discontinuation, then trough FEV1 will be regarded as missing.

If any of the values used in the trough FEV1 are collected within six hours of rescue medication or 7 days of systemic corticosteroid then the individual FEV1 within 6 hours after rescue medication use or within 7 days of systemic corticosteroid will be set to missing. If rescue medication is taken during the 24 hour spirometry assessments then from the time of the rescue medication intake, all post-time point spirometry assessments will be considered as missing in this treatment period.

Subgroup analysis:

The primary analysis will be performed by subgroup of patients based on their compliance of study medication within the 7 days before the spirometry assessment: if spirometry assessment is done during day 14, then compliance will be calculated between day 8 and day 14 on a total number of 7 doses.

This analysis will be provided per compliance of study medication within the 7 days before spirometry assessment defined as follows:

- <80% Compliance of study medication within the 7 days before spirometry assessment (less than a total number of 5 doses)
- 80-100% Compliance of study medication within the 7 days before spirometry assessment (more or equal a total number of 5 doses)

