6.10 Rescue medication

At screening, all patients will be supplied with an inhaled short-acting β_2 -agonist (100 $\mu\text{g}/\text{puff}$ salbutamol or other short-acting β_2 -agonist at matching dose strength) which they will be instructed to use throughout the study as rescue medication. Rescue medication will be procured by the investigative site. Subjects should be instructed to abstain from taking rescue medication within 6 hours of the start of each site visit unless absolutely necessary. If a subject does use their rescue medication within 6 hours of the spirometry assessments on Day 14 in either of the three treatment periods, the spirometry assessments should continue as planned, with the rescue medication usage recorded in the CRF and the data will be excluded from the PD analysis set.

During the study, subjects will record use of rescue medication in a patient diary. Patients should monitor this use carefully and if they use more than ≥ 12 puffs (100 $\mu\text{g}/\text{puff}$) over 24 hours then they should call the site and inform the site personnel. If rescue medication use continues at this level for another 48 hours on two consecutive days then the patient will meet withdrawal criteria ([Section 7.5](#) Study Stopping rules).

Use of rescue medication must be recorded in the patient diary from screening until Day 15 of the Treatment period 3. Concomitant medications and significant non-drug therapies will be collected in the eCRF from screening through completion of the study.

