11.4.3 Handling of missing values/censoring/discontinuations

Subjects withdrawn for any reasons other than safety and tolerability may be replaced on a case by case basis.

If one of the 23h 15 min and 23h 45 min values are missing (or set to missing) then the remaining non-missing value will be taken as trough FEV₁. If both values are missing, or if the subject withdrew from the study, regardless of the reason for discontinuation, then trough FEV₁ will be regarded as missing.

If any of the values used in the trough FEV₁ are collected within six hours of rescue medication then the individual FEV₁ value will be set to missing and the imputation rules stated above will then be applied.

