1.1 Scope of document

The RAP documents contain detailed information to aid the production of Statistics & Programming input into the Clinical Study Report (CSR) for trial “**CQVM149B2203**”.

The Statistical analysis plan (SAP) describes the implementation of the statistical analysis planned in the protocol.

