The PD analysis set will include all subjects with any available PD data, who received any study drug and experienced no protocol deviations with relevant impact on PD data.

The PD analysis set will include all subjects with available PD parameter data who received any study drug and experienced no major protocol deviations with relevant impact on PD data. Any PD data for the primary endpoint obtained within 6 hours after rescue medication use or within 7 days of systemic corticosteroid will be set to missing.

The analysis sets and protocol deviation codes are related as follows:

Table 4-1 Protocol deviation codes and analysis sets

Category Deviation code	Text description of deviation	Data exclusion
Subjects are excluded from Safety analysis in case of these PDs:		
INCL01	Deviation from inclusion criteria: In the unlikely event that a subject was included without written informed consent, then their data will not be used	Exclude subject from Safety analysis set Yes
Subjects are excluded from PD analysis in case of these PDs:		
INCL01	Deviation from inclusion criteria: In the unlikely event that a subject was included without written informed consent, then their data will not be used	Exclude subject from PD analysis set Yes
Subjects are excluded from PK analysis in case of these PDs:		
INCL01	Deviation from inclusion criteria: In the unlikely event that a subject was included without written informed consent, then their data will not be used	Exclude subject from PK analysis sets Yes

If updates to this table are needed, an amendment to the SAP needs to be implemented prior to DBL.

5 Statistical methods for Pharmacokinetic (PK) parameters

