6.2.3.1 Model checking procedures

For the FEV1 AUC (0-4hr) if an observation is missing between two non-missing observations, the AUC will be linearly interpolated between the two non-missing values i.e. the subject's profile will be assumed to be linear between the two available values. Multiple occurrences of such missing values (an observation missing between adjacent non-missing observations) will be handled in a similar manner. But in case of missing consecutive assessments, then the patient profile will be excluded from analysis. No imputation will be made if either the first or the last observation is missing and AUC (0-4hr) is calculated from the available part of the profile ignoring the first and last time points.

For all secondary end points, if a patient takes rescue medication within 6h prior to the spirometry assessments and the visit is not rescheduled to the next day then all spirometry assessments data from this visit and the following visits in this treatment period will be set to missing. If rescue medication is taken during the 24 hour spirometry assessments then from the time of the rescue medication intake, all post-time point spirometry assessments will be considered as missing in this treatment period and AUC (0-4hr) will be considered as missing.

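### After any rescue use in the Day 14/15 profile, SAP 6.1.3.1 discards trough FEV1 values that the protocol's 6-hour rule would keep

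*SAP*

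**What the plan says.** For the primary trough, four places limit deletion after rescue use to 6 hours.

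- Protocol 11.1 and SAP section 4 (both on analysis sets) share the sentence that begins "Any PD data for the primary endpoint obtained within 6 hours after rescue medication use". It sets such data to missing, together with data within 7 days of systemic corticosteroid.
- Protocol 11.4.3 works value by value. For an FEV1 reading collected within six hours of rescue, the individual "value will be set to missing and the imputation rules stated above will then be applied". Those rules let a single remaining reading, at 23h15 or 23h45, serve as the trough.
- SAP 6.1.3.1 repeats the limit for the primary analysis: "then the individual FEV1 within 6 hours after rescue medication use or within 7 days of systemic corticosteroid will be set to missing".

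The next sentence of SAP 6.1.3.1 carries no such limit. If rescue is taken during the 24-hour assessments, "from the time of the rescue medication intake, all post-time point spirometry assessments will be considered as missing in this treatment period". Protocol 11.1 and 11.4.3 contain nothing equivalent. The same rule stands in SAP 6.2.3.1, in a paragraph that opens "For all secondary end points, if a patient takes rescue medication within 6h prior to the spirometry assessments"; there it also makes AUC0-4h missing.

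SAP 1.1 says that the SAP "describes the implementation of the statistical analysis planned in the protocol". Protocol 6.10 says that after rescue within 6 hours of the Day 14 spirometry "the spirometry assessments should continue as planned", and that "the data will be excluded from the PD analysis set".

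**The concern.** Any rescue use within 6 hours before a trough reading necessarily falls inside the 24-hour assessments. The added sentence therefore catches everything that the 6-hour rescue limit catches, and more. For the trough, the preceding sentence keeps a separate effect only through its corticosteroid clause. The SAP as written thus discards primary-endpoint values that the protocol's primary-analysis sections retain.

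This matters if the loss is related to treatment. Protocol 1.3.3.1 reports less rescue use on indacaterol than on placebo in COPD; no asthma rate and no Day 14/15 rate is given. If rescue is commoner on placebo and on days of low FEV1, the deleted troughs are mostly low placebo values. The placebo mean then rises, the treatment difference shrinks and precision falls. Both salt-versus-placebo tests must succeed, and protocol 11.4.6 plans no sensitivity analysis that would show what the deletion rule does.

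**Working it through.** **1. The plan's own figures.** Inputs from protocol 11.7: difference 170 mL, within-subject SD 230 mL, two-sided 5%, 90% power per test.

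- n = 2 × 230² × (1.960 + 1.282)² / 170² = 38.5, so 39; the next multiple of six sequences is 42.
- At n = 42: SE = 230 × √(2/42) = 50.2 mL; noncentrality 170/50.2 = 3.39; with 80 df the power per test is 0.917.
- Joint power: 0.90² = 0.81 is the stated floor. With correlation 0.5 between the two contrasts (shared placebo), it is 0.86 at n = 42.
- Dropout: 42/0.80 = 52.5, so 53; the next multiple of six is 54.

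All stated figures reproduce, and nothing below changes them.

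**2. Where the rules differ.** The trough readings are at 23h15 and 23h45. A 6-hour limit reaches back to 23h15 − 6 h = 17h15 and 23h45 − 6 h = 17h45.

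| Time of a single rescue use | Protocol 11.1 / 11.4.3 | SAP added sentence |
|---|---|---|
| Start of Day 14 profile to 17h15 | both readings kept | no trough |
| 17h15 to 17h45 | 23h45 reading is the trough | no trough |
| 17h45 to 23h15 | no trough | no trough |
| 23h15 to 23h45 | 23h15 reading is the trough | 23h15 reading is the trough |

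Counting from dosing, the rules disagree over 17.75/23.75 = 75% of the time to the last reading.

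**3. Share of rescue users who lose the whole trough** (6-hour rule against added sentence, by assumed timing).

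- Even over 0 to 23h45: 5.5/23.75 = 23% against 23.25/23.75 = 98%.
- All in the first 14 h: 0% against 100%.
- All at 17h15 to 23h45: 5.5/6.5 = 85% against 6.0/6.5 = 92%.

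**4. Joint power under assumed rescue rates.** The documents do not allow this to be computed, so it was simulated over a range: 4,000 trials per scenario, six-sequence three-period crossover, 170 mL for both salts and within-subject SD 230 mL. The model was a REML mixed model with treatment, period and sequence fixed and subject random. Within-subject df were used as an approximation to Kenward-Roger.

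Assumptions not in the documents: rescue rates and timing; between-subject SD 600 mL; a single remaining reading treated as equal to the trough mean; and, where linked, odds of rescue multiplied by 2.7 per SD of low within-period FEV1. Both rules were applied to the same simulated trials.

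With 42 completers and rescue linked to low FEV1, joint power under the 6-hour rule → the added sentence (loss in percentage points) is as follows. Without any deletion it is 0.86.

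| Rescue rate, placebo/active | Even | First 14 h | Late |
|---|---|---|---|
| 2%/1% | 0.854→0.847 (0.7) | 0.854→0.840 (1.4) | 0.854→0.853 (0.1) |
| 5%/2% | 0.853→0.814 (3.9) | 0.860→0.817 (4.3) | 0.820→0.820 (0.0) |
| 10%/5% | 0.838→0.778 (6.0) | 0.858→0.769 (8.9) | 0.783→0.774 (0.9) |
| 20%/10% | 0.834→0.670 (16.4) | 0.852→0.656 (19.6) | 0.692→0.671 (2.1) |

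- Not linked to FEV1, the losses (even/early/late) are 1.2/1.3/0.0, 1.3/2.3/0.4, 4.2/5.9/0.5 and 9.6/12.0/0.9.
- With 54 randomised, 12 of them contributing one or two periods (linked), they are 1.5/1.4/0.1, 3.0/4.2/0.3, 5.9/8.7/0.8 and 14.4/20.0/2.1.
- The Monte Carlo SE of each joint power is below 1 point, so differences of under 1 point between scenarios are noise.

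**5. Bias.** With a true difference of 170 mL, linked rescue and even timing, the estimate under the added sentence is 168, 164, 160 and 152 mL at the four rates: toward zero.

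**The case against.** *The plan is executable.* Both sentences of SAP 6.1.3.1 can be applied together and give one dataset, because the stricter one simply governs. This stands. A reader might infer that the primary analysis is undefined or self-contradictory; the text does not support that. What remains is a departure from the protocol rule and a 6-hour limit that does nothing for the trough.

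*The change may be declared elsewhere.* The SAP is an amendment, some of its pages were removed and others are blacked out. This also stands. A reader might infer an undisclosed change, but one can say only that the visible text does not declare it.

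*Protocol 6.10 may be the source.* Its clause excluding data could mean the affected values or something wider, and on a wide reading it deletes more than 11.4.3 does. But its trigger is also tied to 6 hours. It does not state a deletion of all later readings whatever the interval, so it does not supply the SAP rule. Its ambiguity is a further reason to reconcile the sections.

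*The rule is conservative and the cost is hypothetical.* Largely fair. Deleting low placebo values would not inflate efficacy, and every power loss above rests on assumed rates, timing and linkage. The 20-point extreme needs 20% placebo rescue within one profile, all of it in the first 14 hours, and nothing in the documents suggests that. Nor may one infer that the trial is underpowered as planned.

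**Conclusion.** The point holds as a mismatch between SAP and protocol on a primary-endpoint data rule. SAP 6.1.3.1 loses the trough for rescue at any time up to 17h45 post-dose, where protocol 11.1 and 11.4.3 keep it in full (to 17h15) or from one reading (17h15 to 17h45). This follows from the documents alone.

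The cost is unknown because no Day 14/15 rescue rate is given. Under the assumed rates, the loss of joint power is up to about 1.5 points if rescue is rare (2%/1%) and about 2 points or less if it is late. It becomes larger, up to about 20 points, only if rescue is both frequent and before 17h45. Any bias is plausibly toward zero, on the assumption that rescue is commoner on placebo and on low-FEV1 days. It should be corrected because the values are collected, the protocol keeps them, and their loss may depend on treatment.

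**What to change.** Before database lock:

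- **SAP 6.1.3.1.** For trough FEV1, apply the protocol rule: individual values within 6 hours after rescue or within 7 days of systemic corticosteroid are set to missing, all others are kept, and a single remaining reading serves as the trough. Remove the added sentence or keep it only as a named sensitivity analysis. If the sponsor prefers the stricter rule, declare it as a change from the protocol and report the 6-hour rule alongside.
- **Reporting.** Tabulate rescue-related trough deletions by treatment.
- **Protocol 6.10.** State which data its exclusion clause covers, and reconcile it with 11.4.3.

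Separately, for secondary endpoints only: SAP 6.2.3.1, read literally, discards a complete AUC0-4h when rescue is taken after 4 hours. Limit that deletion to rescue that affects the 5 min to 4 h readings. The same paragraph provides for moving the visit to the next day and for deleting subsequent visits in the period; reconcile this with protocol 6.10, under which spirometry goes ahead.

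The cost is SAP wording, one table and a one-line protocol clarification. No new data are needed.

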6.1.3.2 Graphical presentation of results

Individual time profiles and the results of statistical analysis will also be presented in a graphical representation called forest plot showing the estimated mean differences in dacetorol salts (acetate and maleate) to placebo and estimated difference between acetate and maleate salts and their confidence intervals per time point for each comparison.

6.2 Secondary objectives

6.2.1 Variables

Forced Expiratory Volume in 1 second (FEV1), 3 seconds (FEV3), 6 seconds (FEV6), FEV1% predicted, Forced Vital Capacity (FVC), FVC% predicted and Forced Expiratory Flow 25-75% (FEF25-75%) will be measured at screening, pre-dose, and specific time points for approximately 24 hours post dose (on Days 14 and 15) in each treatment period. Additional lung function parameters will be derived mathematically from the listed measurements (e.g. FEV1/FVC, FEV1/FEV6, FEV3/FVC, FEV3/FEV6, 1-FEV3/FVC, 1-FEV6/FVC).

For each patient, the spirometric measurements must be taken at approximately the same corresponding time of day in each treatment period as closely as practically possible.

Pre-bronchodilator FEV1, FEV3, FEV6, FVC, and FEF25-75 assessments will be conducted at screening.

Spirometry timepoints following the last dose of study medication in each treatment period are as follows:

- Day 14 predose: - 45 min and -15 min
- Day 14/15 post-dose: 5 min, 15 min, 30 min, 1 h, 2 h, 3h, 4 h, 8 h, 12 h, 23 h 15 min, 23 h 45 min

Time to peak FEV1 (maximum FEV1 post treatment) on Day 14 will be derived from the spirometry timepoints following the last dose of the study medication in each treatment period.

Standardized FEV1 AUC (0-4hr) (i.e. Area Under Curve between 5 min (=time 0h) and 4h post dose) on Day 14 of treatment. Area under curve for FEV1 from Spirometry data and will be calculated by trapezoidal rule as follows:

$$AUC_{0-T} = \frac{\sum_{i=1}^n (t_i - t_{i-1}) * (c_i + c_{i-1})}{2}, \text{ with } t_0 = 0 \text{ and } t_n = T$$

Where 't' is time-point and 'c' is FEV1 at time-point t.

T0 is initial time-point, Tn is the last time point of interest.

Peak FEV1 defined as the highest bronchodilatory effect on FEV1 during a period of 5 min to 4h on Day 14 of treatment. FEV1 measurements to consider defining peak FEV1 are on day 14 +5 min, +15 min, +30 min, +1h, +2 h, +3h, +4h.

PEF will be recorded twice daily using a Peak Flow Meter device, once in the morning and once approximately 12 h later in the evening. The morning/evening and overall (average of both morning and evening) PEF measurements will be averaged separately between days 8 to 14 of each treatment period and each subject.

The number of puffs of rescue medication taken is recorded twice (morning/evening) by subjects in the eDiary. The morning/evening and overall (both morning and evening) number of puffs of rescue medication will be averaged separately between days 8 to 14 of each treatment period and each subject.

Below is an example for averaging the rescue medication for each treatment period and subject.

Subject	Day	Rescue Medication		
		Morning	Evening	Overall
5101	8	7	5	12
5101	9	6	8	14
5101	10	5	6	11
5101	11	6	7	13
5101	12	4	8	12
5101	13	9	6	15
5101	14	4	4	8

Corporate Confidential Information

6.2.2 Descriptive analyses

All the above secondary variables will be listed by treatment sequence, subject and visit/time and descriptive summary statistics will be provided by treatment and visit/time. Summary statistics will include arithmetic mean, SD, CV (arithmetic), median, minimum and maximum.

The mean morning/evening and overall number of puffs of rescue medication use will be listed by treatment sequence and subject and summary statistics by treatment. The number and percentage of subjects with rescue medications, together with the number of puffs, will be tabulated by treatment.

The average morning/evening and the overall PEF (L/min) will be listed by treatment sequence and subject and summary statistics by treatment.

6.2.3 Statistical model, assumptions and hypotheses

All the above secondary variables (Section 6.2.1) for spirometry (excluding Time to peak FEV1, Standardized FEV1 AUC (0-4hr), Peak FEV1, Average rescue medication for morning/evening and Average PEF measurements for morning/evening) after 14 days of treatment will be analyzed using repeated measures of ANOVA including treatment, period, sequence, time, treatment by time as fixed effects and subject nested within sequence will be included as a random effect. Time will be repeated within each subject*period interaction term. An unstructured variance unstructured covariance matrix will be applied.

Standardized FEV1 AUC (0-4hr) between baseline (pre dose) and 4h post dose and peak FEV1 on Day 14 of treatment will be analyzed using the same model (ANOVA) as for the primary analysis.

Averaged morning/evening and overall number of puffs of rescue medication and average morning/evening and overall number of PEF measurements will be analyzed using the same model (ANOVA) as for primary analysis.

Time to peak FEV1 on Day 14 will be analyzed using non-parametric methods. The median difference and the two-sided 95% confidence interval of the median difference in time to peak FEV1 will be estimated using Hodges-Lehmann estimation procedure.

6.2.3.1 Model checking procedures

For the FEV1 AUC (0-4hr) if an observation is missing between two non-missing observations, the AUC will be linearly interpolated between the two non-missing values i.e. the subject's profile will be assumed to be linear between the two available values. Multiple occurrences of such missing values (an observation missing between adjacent non-missing observations) will be handled in a similar manner. But in case of missing consecutive assessments, then the patient profile will be excluded from analysis. No imputation will be made if either the first or the last observation is missing and AUC (0-4hr) is calculated from the available part of the profile ignoring the first and last time points.

For all secondary end points, if a patient takes rescue medication within 6h prior to the spirometry assessments and the visit is not rescheduled to the next day then all spirometry assessments data from this visit and the following visits in this treatment period will be set to missing. If rescue medication is taken during the 24 hour spirometry assessments then from the time of the rescue medication intake, all post-time point spirometry assessments will be considered as missing in this treatment period and AUC (0-4hr) will be considered as missing.

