2.2 Secondary objective(s)

Secondary objective(s)	Endpoints related to secondary objective(s)

To assess the steady state pharmacokinetics of indacaterol after 14 days of treatment of orally inhaled indacaterol salts (maleate and acetate) in subjects with asthma.	
AUC_{0-24h,ss} and C_{max,ss}, T_{max,ss}, C_{min,ss}, C_{a,v,ss} and F_{rel}

To assess the bronchodilator effect of orally inhaled indacaterol salts (maleate and acetate) in subjects with asthma compared to placebo as measured by:
Time to peak FEV₁ on Day 14FEV₁, FEV₁ (% predicted), FVC, FVC (% predicted), FEV₁/FVC, and FEF_{25-75%} at each post-dose time point after 14 days of treatmentStandardized FEV₁ AUC from pre-dose to 4 h post-dose on Day 14 of treatment	
FEV₁, FVC, and FEF_{25-75%} after 14 days of each treatment period

To assess the bronchodilator effect of indacaterol acetate, indacaterol maleate, and placebo by comparing the pre-medication (morning (pre-dose) and evening) peak expiratory flow (PEF) rate collected between days 8 and 14 of each treatment.	
Peak expiratory flow rate collected daily between days 8 and 14 during all three treatment periods (indacaterol acetate, indacaterol maleate, and placebo)

To assess rescue medication usage for indacaterol salts (maleate and acetate) in comparison to placebo.	
Usage of rescue medications as reported by subjects via diary during each treatment arm

[figure not shown]
Secondary objective(s)	Endpoints related to secondary objective(s)

• To assess the safety and tolerability of indacaterol salts (maleate and acetate) in comparison to placebo of 14 days of treatment in each treatment period.	
• Safety assessments during each treatment period including:
• Adverse Events and Serious Adverse Events• Vital signs• Hematology• Blood Chemistry• Urinalysis• ECG evaluation

Corporate Confidential Information

3 Investigational plan

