1.3.2 Secondary objective(s)

- To assess the steady state pharmacokinetics of indacaterol after 14 days of treatment of orally inhaled indacaterol salts (maleate and acetate) in subjects with asthma.
- To assess the bronchodilator effect of orally inhaled indacaterol salts (maleate and acetate) in subjects with asthma compared to placebo as measured by:
 - Time to peak FEV1 on Day 14
 - FEV1, FEV1 (% predicted), FVC, FVC (% predicted), FEV1/FVC, and FEF25-75% at each post-dose time point after 14 days of treatment
 - Standardized FEV1 AUC from pre-dose to 4 h post-dose on Day 14 of treatment
- To assess the bronchodilator effect of indacaterol acetate, indacaterol maleate, and placebo by comparing the pre-medication (morning (pre-dose) and evening) peak expiratory flow (PEF) rate collected between days 8 and 14 of each treatment.
- To assess rescue medication usage for indacaterol salts (maleate and acetate) in comparison to placebo.
- To assess the safety and tolerability of indacaterol salts (maleate and acetate) in comparison to placebo of 14 days of treatment in each treatment period.

Corporate Confidential Information

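### The standardized FEV1 AUC (0-4 h) has no stated time divisor; programmed as written, an isolated missing 4 h reading enters the ANOVA about 25% too low

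*SAP*

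**What the plan says.** **Definition.** SAP 6.2.1 describes the endpoint as "Standardized FEV1 AUC (0-4hr) (i.e. Area Under Curve between 5 min (=time 0h) and 4h post dose) on Day 14 of treatment". It continues: "Area under curve for FEV1 from Spirometry data and will be calculated by trapezoidal rule as follows". The formula multiplies each time step by the sum of the two adjacent FEV1 values, adds these up and halves the total, with t0 = 0 and tn = T. The result is in L·h. No division by T or by (tn − t0) follows, and no visible passage of the protocol or SAP defines *standardized*.

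**Missing readings.** SAP 6.2.3.1 interpolates a single interior gap. For the ends of the profile it says "No imputation will be made if either the first or the last observation is missing", and then that "AUC (0-4hr) is calculated from the available part of the profile ignoring the first and last time points". Two rules limit the exposure. For adjacent gaps: "But in case of missing consecutive assessments, then the patient profile will be excluded from analysis". And rescue use during the profile sets the AUC to missing.

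**Analysis.** SAP 6.2.3 puts the result into the primary ANOVA. According to SAP 6.1.3, its terms are treatment, period, sequence and subject within sequence.

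**Window.** SAP 6.2.1 starts at 5 min. SAP 6.2.3 has "Standardized FEV1 AUC (0-4hr) between baseline (pre dose) and 4h post dose", SAP 1.3.2 has "Standardized FEV1 AUC from pre-dose to 4 h post-dose on Day 14 of treatment", and protocol 2.2 has "AUC from pre-dose to 4 h post-dose on Day 14 of treatment". Protocol 11.5.1 starts at screening, with pre-dose in brackets.

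**3 h reading.** Protocol 8.5.1 and SAP 6.2.1 list a 3 h spirometry. The detailed schedule table in protocol 8.1, as extracted, goes from 2 h to 4 h.

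**The concern.** A trapezoid sum grows with the length of the profile. If one profile stops at 3 h because the 4 h reading is missing, its sum covers three hours while the others cover four. The ANOVA has no term for profile length, so it would treat the shortfall as lower lung function. If such gaps fall more often in one arm, the treatment contrast is biased. If they are balanced, the error variance rises.

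The name of the endpoint suggests that a division by time was intended. The choice of divisor still matters: with a fixed 4 h, the truncated profile stays too low by the same proportion. The end-point rule can also be read in two ways, dropping only the missing end or dropping both ends.

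**Working it through.** The documents state no figure for this AUC, so there is none to reproduce.

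**Inputs.** Time grid from SAP 6.2.1: 5, 15, 30 min, 1, 2, 3, 4 h. FEV1 level: not in the documents; a flat profile of 2.0 to 3.0 L is assumed. For a flat profile the percentage loss is lost time divided by total time and does not depend on the level.

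**Step 1: loss in one affected profile.** The window is 4 h if 5 min is relabelled 0 h, as SAP 6.2.1 does, and 4 − 5/60 = 3.917 h on clock time.

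| Gap | 5 min = 0 h | Clock time |
|---|---|---|
| 4 h missing, 3 h collected | 1/4 = 25.0% | 1/3.917 = 25.5% |
| 4 h missing, no 3 h reading scheduled | 2/4 = 50% | 2/3.917 = 51.1% |
| 5 min missing | 0.25/4 = 6.25% | 0.167/3.917 = 4.3% |
| Both ends dropped, 3 h collected | 1.25/4 = 31.25% | 1.167/3.917 = 29.8% |

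If the window starts pre-dose, 5 min is an interior point and is interpolated, so the 5 min row disappears. The 4 h loss remains, at 1/4 = 25% (pre-dose value placed at 0 h) to 1/4.75 = 21% (start at −45 min), with 3 h collected. If a 3 h reading is scheduled but also missing, the rule on consecutive gaps would exclude the profile.

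**Step 2: choice of divisor.** Flat 2.5 L, 5 min = 0 h, 4 h missing: the sum is 2.5 × 3 = 7.5 L·h.
- No divisor: 7.5 against 10.0 L·h for a complete profile.
- Fixed 4 h: 7.5/4 = 1.875 L against 2.5 L, still 25% low.
- Observed interval: 7.5/3 = 2.5 L, correct.

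For a profile that is not flat, a small error remains after division by the observed interval. With a rise of 50 to 200 mL over the window it is 4 to 25 mL low with 4 h missing, and 2 to 9 mL high with 5 min missing. For example, a steady rise of 200 mL averages 100 mL above its start over 4 h and 75 mL over 3 h, a difference of 25 mL. A falling profile gives the opposite sign.

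**Step 3: scale for the group contrast, illustration only.** The documents give no planning values for this AUC. The trough values in protocol 11.7 are borrowed: 170 mL × 4 h = 0.68 L·h, SD 230 mL × 4 h = 0.92 L·h, and 42 completers. The SE of a contrast is 0.92 × √(2/42) = 0.201 L·h. A missing 4 h reading at 2.0 to 3.0 L costs 2.0 to 3.0 L·h.
- One affected placebo profile of 42 raises the contrast by 2.0/42 to 3.0/42 = 0.048 to 0.071 L·h. That is 7.0 to 10.5% of 0.68, or 0.24 to 0.36 SE.
- One affected active profile lowers it by the same amount. In 5,000 simulated crossover data sets per case (six sequences of seven subjects; subject, period and treatment effects), power for that contrast fell from about 0.92 to 0.87–0.83.
- One such gap in each arm gave no bias, but the SE rose from 0.200 to 0.211–0.224 L·h.

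**The case against.** The strongest reply is that this is an undefined term and not a wrong analysis. The endpoint is called *standardized* throughout, the formula is labelled as the area only, and a programmer who reported the bare sum would be ignoring the endpoint's name. Parts of both documents are blacked out, including text at the end of SAP 6.2.1 and of protocol 8.5.1, so the division may be stated where we cannot see it. This stands as a limit: the claim is about the visible text and is conditional on how it is programmed. It does not remove the point, because the label (0-4 h) invites a fixed divisor of 4 h, which leaves the error in place.

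Exposure is also narrow. Subjects are in the clinic on Day 14, and the rules on rescue use and consecutive gaps remove many incomplete profiles. SAP 6.2.2 and 6.2.3.2 plan listings, minimum values, individual profiles and studentized residual plots. On the borrowed SD, a loss of 2.0 to 3.0 L·h is about 2.2 to 3.3 SD (2.0/0.92 and 3.0/0.92), so it may well be noticed. But no action is specified for that case, and a correction made after unblinding would be post hoc.

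A reader might infer that affected values are wrong whatever is programmed, or that the AUC comparison will lose a known amount of power. The documents support neither. The first depends on the divisor. For the second, no rate of missing end readings is given, and no power is stated for this endpoint: protocol 11.8 covers pharmacokinetics only.

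**Conclusion.** The point holds conditionally. If the SAP 6.2.1 sum is programmed as written, or divided by a fixed 4 h, an isolated missing 4 h reading not due to rescue use gives a value about 25% too low, or about 50% if no 3 h reading is collected. A missing 5 min reading gives about 4-6%, and only with a window that starts at 5 min. These percentages assume a roughly flat profile. The percent-of-effect and power figures also assume an FEV1 level, a number of affected profiles and trough planning values, and serve for scale only.

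Complete profiles are only rescaled, so a comparison based on them alone is unchanged. Bias needs gaps that differ by arm; balanced gaps cost precision. This is one secondary endpoint, and the primary trough FEV1 test is not affected. It should be fixed because the written rules can produce an error that reflects missing time and not lung function, and the repair is small. The differing window starts and the 3 h reading are separate points on the same endpoint. The absent 3 h row may be an artefact of table extraction and needs a check before it is called a contradiction.

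**What to change.** 1. **SAP 6.2.1:** state that the trapezoid sum is divided by the interval actually observed, t_last − t_first, on the same time scale as the sum. The endpoint is then a time-averaged FEV1 in litres.
2. **SAP 6.2.3.1:** state that only the missing end point is dropped. A minimum-coverage rule is optional and for the sponsor to decide.
3. **Window start:** reconcile SAP 6.2.1 with SAP 1.3.2, SAP 6.2.3, protocol 2.2 and protocol 11.5.1. This also settles whether 5 min is an end point or an interior point.
4. **3 h reading:** check whether the schedule table in protocol 8.1 contains the 3 h spirometry listed in protocol 8.5.1 and SAP 6.2.1, and align them if it does not.

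Items 1 and 2 are a SAP edit before database lock and need no new data. Any change to the protocol text or schedule table under items 3 and 4 needs a written amendment with the approvals in protocol 13.1.
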